#### **CGM-based education and coaching**

This part of the study will be implemented by coaches who have undergone diabetes management training that incorporates device information, educational content, and techniques based on behavioral discussion and patient self-learning/empowerment. Coaches will also be equipped to help patients use activity data in conjunction with their CGM use. Coaches will receive training regarding human research subjects to insure the ethical treatment and safety of all participants. All training will be reinforced during contact with study staff.

The information contained in the Standard of Care document has been approved by the study's Medical Directors (co-investigators) as providing fundamental diabetes self-management information to patients with T2D. In the Standard of Care document, patients are instructed that this information does not replace individual guidance given to patients from their providers.

Each participant will be assigned a coach who will provide education and support by phone and secure text messaging. During weeks when patients are using the CGM system, they will be scheduled to receive a weekly phone call from their coach. Otherwise, patients can reach out to their coach by leaving a voicemail for the coach. Coaches will return calls within two business days. Education will be centered around the four educational objectives (food intake and PPG, walking to reduce PPG, medication adherence, and nighttime glucose monitoring) and reinforcement of messages in the patient standard of care document. The coach will provide education on how to optimally use the RT-CGM system for self-discovery, focusing on effective times to look at the RT-CGM and behaviors that are likely to impact the CGM (outlined above). Coaches will assist participants in setting personalized goals and act as a

sounding board for participants to discuss their self-discoveries. Coaches will review with patients the Rule of 15 to deal hypoglycemic episodes.

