## Program Length

Participating patients will be asked to use a CGM system and an activity tracker for 10 weeks. After the 10 weeks, patients may be offered the opportunity to continue to use their smartphones and activity trackers as long as they continue to sync the tracker at least every three weeks through August 31, 2018.

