#### [Program devices](#)

##### [Dexcom CGM System](#)

Patients in this study will employ an investigational-use only (IUO) CGM system manufactured by Dexcom, Inc. (San Diego, CA). The devices in this system (a sensor with auto-applicator, a transmitter, and a mobile application) represent a variation of the Dexcom G6 CGM system which received approval by the FDA under an investigational device exemption (IDE) on April 28, 2016. In 2017, Chesapeake IRB designated the device as a Non-Significant Risk device for our research protocol Pro00021722. The ways in which these study devices vary from the G6 system and the commercial G5 system are described here as well as in the attached Investigator's Brochure.

The investigational system represents several improvements over the commercially-available Dexcom CGM systems. The investigational applicator is designed to improve ease of use and reduce the risk of user error compared to Dexcom's G5 commercial device by simplifying the application process. While the commercial device requires the user to perform multiple actions to deploy the sensor-delivery needle, retract the needle, and release the applicator from the transmitter holder, the investigational applicator performs all of these steps with just one action by the user.

The investigational sensor has a lifetime of 10 days, as opposed to the 7-day lifetime of Dexcom's commercial G5 sensor. As a result, users will not need to change their sensors as often, further reducing risk for any difficulties or inconvenience associated with sensor application. The sensor has also been redesigned to reduce sensor error associated with the use of acetaminophen, thus improving the reliability of sensor readings.

Compared to the Dexcom G6 transmitter, the IUO transmitter has a lower design profile to improve everyday wearability.

The mobile (smartphone) app displays glucose information in real-time. To maintain the accuracy of these readings, the system must be calibrated periodically based on fingerstick readings from a blood glucose meter. After initial calibrations, the investigational app requires less frequent calibrations than

the commercial device. While the commercial system requires calibration every 12 hours, after the first day the investigational system requires calibration every 24 hours. This improvement is expected to further improve the usability and acceptance of the CGM system.

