## Patient Participation

All program participants will participate at-will and have the freedom to terminate their participation at any time. Participants, including those who intend to withdraw from the program or those who have withdrawn will be able to access program coaches for assistance with any program-related questions or issues.

During the time that patients use the CGM system, coaches will schedule weekly calls with them. If patients demonstrate by their actions that they no longer want to participate in the study by no longer syncing their CGM or activity tracker data, outbound call or text messaging efforts will be made to reach the patient. If after three weeks there has been no data received and no communication with the patient, a voicemail will be left asking patients to reply within three days or they will be considered dropped from the study. No response to these voicemails will result in the shipment to these patients of a postage-paid box and a letter. The letter will inform patients that they are considered as non-participating and need to return the CGM devices, activity tracker, and smartphone.

During the course of the program, should any participant report medical issues that may affect that patient's ability to participate in the program, the patient will be directed to consult with his/her physician.

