- None of the expected device-related adverse events as defined in the protocol and associated documents would be life-threatening or would result in any permanent impairment of a body function or permanent damage to a body structure;
- There are no expected electrical safety risks as the device has passed the electrical safety tests as per EN45502-1 and EN60601;
- If the subject feels any discomfort during the course of the study, he/she will be able to remove the device immediately (the device is not permanent);
- The device is being used to complement, not replace, self-monitoring of blood glucose meter information, and readings are not intended to be used alone to make diabetes self-management decisions. As with the currently approved device and per intended use of similar technologies, subjects in the study will be instructed not to use the device for diabetes therapy or management;

- Subjects will be instructed to monitor their blood glucose levels as per their usual practice.

Adverse events (AE) associated with the use of the device include pruritus (severe itchiness present 48 hours after removal), erythema (reddening of the skin present 48 hours after removal), and inflammation (swelling and pain, defined as 8 or greater on a 10 point scale 48 hours after removal) where the adhesive touches the skin; local infection at insertion site; and shooting pain located at the site of the sensor (defined as 8 or greater on a 10 point scale). Rarely, the sensor wire will fracture when the sensor is being inserted, worn, or removed. If a sensor breaks and no portion of it is visible above the skin, the participant will be instructed to not remove it and seek medical care from the study doctor and/or his staff.

No serious adverse events (SAE) or Unanticipated Problems (UP) are expected as a result of participation in this minimal risk study. However, AE, SAE and UP will be monitored in the following ways:

- Participants in the study will be instructed to call the study doctor's clinical research coordinator to report all AE, SAE and UP related to the use of the CGM devices. The study doctor and/or his staff will assess the severity of any health problems associated with the device, and if needed, see the patient at the study clinic to assure appropriate care.

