### Risks of CGM

When the wire-like sensor is deployed by the applicator, participants can expect a sensation similar to a needle insertion for a blood draw. Risks of CGM use include discomfort during sensor insertion, along with pain, inflammation, redness, swelling, minor bleeding and minor infection at the sensor insertion site. Participants might also experience these symptoms as a result of contact between the adhesive pad of the sensor and the skin. In rare cases, an infection can spread to other parts of the body.

Allergic reactions can develop in response to the sensor, the adhesive, and other parts of the CGM. If these symptoms occur, participants have the ability to remove the CGM at will and can anticipate that their symptoms will clear up within one week.

The sensor and/or applicator may fracture during use. If a sensor remains in the skin, there is minimal risk to the patient as long as a physician confirms there are no symptoms of infection or inflammation.

Patients will be advised that the investigational sensor, transmitter, and smartphone must be removed before Magnetic Resonance Imaging (MRI), Computed Tomography (CT) scan, or diathermy treatment. The device is MR Unsafe. Participants should not bring any portion of the device into the MRI environment. The Dexcom IUO CGM System has not been tested during MRI or CT scans or with diathermy treatment. The magnetic fields and heat could damage the device, causing it to stop displaying glucose readings, display inaccurate glucose readings, or prevent alerts.

Patients will also be advised of CGM system warnings that may affect the proper operation of the device and/or the patient's safety. These warnings will be described in the informed consent and authorization form, and in the informational materials provided to patients when they receive their systems.

Patients will be provided with a phone number for Dexcom's Technical Support. Staff for this line will be well-qualified to address any potential questions and risks associated with the investigational device. Significant or serious health risks with CGM are not anticipated.

The same precautions have been taken to code and/or encrypt the investigational system's electronic data as have been taken with the commercial Dexcom devices. Regardless, throughout the program, patients will be advised not to rely on the device to make any treatment decisions, and to measure their blood glucose in order to confirm any symptoms of hypoglycemia.

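### No scheduled coach call reaches the 48-hour point that defines skin reactions for a completer's last sensor, and none is assured for those who stop early

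*Combined protocol and SAP*

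**What the plan says.** **Length of CGM use.** Program Length: "Participating patients will be asked to use a CGM system and an activity tracker for 10 weeks". The Dexcom CGM System section adds: "The investigational sensor has a lifetime of 10 days".

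**Scheduled contact.** Section 6 (CGM-based education and coaching): "During weeks when patients are using the CGM system, they will be scheduled to receive a weekly phone call from their coach". Outside those weeks the initiative passes to the participant: "Otherwise, patients can reach out to their coach by leaving a voicemail for the coach". Section 7 (Patient Participation) repeats the limit: "During the time that patients use the CGM system, coaches will schedule weekly calls with them".

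**Definition of the skin events.** Section 9 defines three of its sensor events by their state 48 hours after removal, for example "erythema (reddening of the skin present 48 hours after removal". Pruritus and inflammation carry the same condition. Local infection and shooting pain do not. Section 12 (Risks of CGM) says participants who remove the device "can anticipate that their symptoms will clear up within one week".

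**After the last sensor.** Figure 2 lists a coach's summary report, a survey and return of equipment. The Section 10 data table and its footnote allow the exit survey to be done by post or by phone. No day and no adverse-event item is stated for the report or the survey. Section 6 (Dexcom CGM System) permits coaches to contact participants during the study but does not require it.

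**When data stop.** Section 7 provides for calls or texts without giving a date. After three weeks without data or communication comes a voicemail with three days to reply, then a return box and letter: "The letter will inform patients that they are considered as non-participating and need to return the CGM devices, activity tracker, and smartphone".

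**The concern.** Three of the skin events are defined at a time that, for the last sensor, comes after the weekly calls have finished. Earlier sensors do not have this problem, because calls continue after each removal.

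The coaches' part in safety reporting (Section 9) is to listen for complaints while talking to participants. Once the calls stop, that route depends on someone choosing to make contact. The last site may also be an informative one. Section 12 reminds participants that they may take the sensor off if they have symptoms, and permanent removal also ends the scheduled calls. Section 14 pays $190 of the $250 maximum for the first 10 days, so stopping after one sensor is a plausible pattern. The sensor is investigational and Section 9 sends its adverse events to the IRB, the manufacturer and the FDA, so how completely they are found matters even in an exploratory study.

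**Working it through.** The plan states no figure to reproduce. The check is calendar arithmetic in whole days.

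**Inputs**
- CGM period: 10 weeks (Program Length), so 10 × 7 = 70 days.
- Sensor life: 10 days (Dexcom CGM System).
- Calls: one a week, only in weeks of CGM use (Sections 6 and 7).
- Skin-event point: 48 hours after removal (Section 9).
- Enrolment: 500 (Section 7).

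**1. Number of sensors.** 70 / 10 = 7. The compensation schedule agrees: $190 + 6 × $10 = $250, the stated maximum.

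**2. The last sensor of a completer.** With continuous wear it comes off on day 70. The 48-hour point is day 70 + 2 = 72, and one week is day 77. If calls fall on day c of each week (c = 1 to 7), the tenth and last is on day c + 63, which is day 70 at the latest. No choice of weekday gives a call on or after day 72.

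**3. Sensors 1 to 6.** Removals fall on days 10, 20, 30, 40, 50 and 60. For each of the seven call weekdays, the first call at least 48 hours later comes 2 to 8 days after removal. It comes on the eighth day in 6 of the 42 sensor-by-weekday combinations. Each earlier sensor therefore has a scheduled call after the 48-hour point, though not always within a week.

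**4. Share affected at full wear.** 1/7 = 14.3% of a completer's sites. Over 500 completers, 500 of 500 × 7 = 3,500 sites.

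**5. Early stoppers.** Someone who stops after k sensors has at most 1 in k sites without a scheduled call at 48 hours or later. This is an upper bound. Let the last sensor come off on day r of the final week of use and that week's call fall on day c. The call is at least 48 hours later when c − r ≥ 2. For r = 1 to 7 the number of qualifying call days is 5, 4, 3, 2, 1, 0, 0, a total of 15 of 49 (31%). That percentage assumes both days are uniform over the week and the call is still made after the sensor is off.

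**6. Silent participants.** The first dated step is at 21 days, and the reply period ends at 21 + 3 = 24 days. Both are later than the one-week resolution figure. The calls or texts that come before have no date.

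**7. Section 9 against Appendix B.** Appendix B grades redness, itch, pain and swelling on 1-to-10 scales with no 48-hour condition. Its relatedness question rates a former sensor site as probably not related once the sensor has been off for two days or more, which is when the Section 9 definitions begin to apply. A reaction on the last site could therefore be classed differently under the two texts.

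**The case against.** The weekly calls are educational and are not the adverse-event system. Participants are told to ring the research coordinator about any device event, with no end date. Reports to the manufacturer's support line are passed on. Coaches stay reachable for the study, including by those who withdraw, and a report and a survey follow the 10 weeks. A reaction present at 48 hours can be reported later, and one that prompts removal began while calls were running. The plan does not say that coaches ask about skin reactions, so sensors 1 to 6 may have no active questioning either. All of this stands. It limits the point to scheduled contact, but it supplies no dated check after the last removal.

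A reader might infer more than the documents support:
- **That every participant's last sensor is missed.** Wear need not be continuous (Section 14), and a call later in the final week of use can fall at 48 hours or more.
- **That all contact ends with CGM use, or that silent participants hear nothing for three weeks.** Section 7 provides for calls or texts before the voicemail.
- **That late events fall outside a defined collection window.** None is defined. Section 9 gives a persistence criterion and Section 12 an expectation about recovery.
- **That reported adverse-event rates will be biased down by a known amount.** Section 10 plans no adverse-event rate, and no figure in the documents sizes the loss.

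The Appendix C reporting chart is not legible in the available copy, and the complaints guidebook and case report form are not included. A dated check could be in one of them.

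**Conclusion.** The point holds for scheduled active contact. For a participant who wears sensors through day 70, no scheduled coach call falls at or after the 48-hour point for the last sensor. For those who stop early, none is assured. The extent is up to 1 of 7 sites per completer (up to 500 of 3,500 at full wear), and at most 1 in k for someone who stops after k sensors.

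These figures assume continuous 10-day wear, one call a week on a fixed weekday and no call after the week of last use. They count sites without a scheduled call, not missed events. The finding covers pruritus, erythema and inflammation only, because infection and shooting pain have no 48-hour condition. It is a modest weakness in how safety data are gathered for an investigational sensor, and it is worth correcting because the correction is cheap.

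**What to change.** - **Date the exit contact.** In Figure 2, CGM-based education and coaching, Patient Participation and the Section 10 data table, time the existing exit survey to between 48 hours and about one week after the last sensor comes off, by coach phone call where possible. Apply this to completers and to those who withdraw, are removed or are dropped.
- **Add two questions.** Ask about any site reaction and the reason for stopping.
- **Cover those not reached.** Put the same two questions and the coordinator's number in the letter that goes with the return box.
- **Reconcile the definitions.** Section 9 and Appendix B must be brought into agreement on whether the 48-hour condition applies and on how relatedness is rated for a site whose sensor is already off.

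**Cost.** The survey and the letter already exist, and coaches may already give the survey by phone. At worst this adds 500 short calls to the 500 × 10 = 5,000 scheduled, or 500 / 5,000 = 10%, made by the same coaches.

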#### [Integration with patient care](#)

Throughout the program, patients will be instructed to follow their normal care plan as directed by their physicians and as consistent with ADA 2017 standard-of-care guidelines. This includes taking medications as prescribed; engaging in physical activity—especially walking after meals; eating a diet that optimizes glucose control through food choice and timing; responding to hypoglycemia symptoms with a fingerstick and consuming a pre-determined amount of glucose; and monitoring emotional wellness. By providing a continuous graph of each participant's glucose, the CGM system illustrates how the above-described glucose management behaviors impact the participant's glucose.

Should patients in the course of the program experience any health problems associated with the use of their CGM devices, they will be directed to contact the study doctor's clinical research coordinator. The coordinator will assess the severity and relatedness of the event and arrange for appropriate care. Should patients mention a potential study-related health concern to their coach, the coach will actively work to assure the patient speaks with the study doctor, either through a warm transfer or callback.

#### [Program devices](#)

##### [Dexcom CGM System](#)

Patients in this study will employ an investigational-use only (IUO) CGM system manufactured by Dexcom, Inc. (San Diego, CA). The devices in this system (a sensor with auto-applicator, a transmitter, and a mobile application) represent a variation of the Dexcom G6 CGM system which received approval by the FDA under an investigational device exemption (IDE) on April 28, 2016. In 2017, Chesapeake IRB designated the device as a Non-Significant Risk device for our research protocol Pro00021722. The ways in which these study devices vary from the G6 system and the commercial G5 system are described here as well as in the attached Investigator's Brochure.

The investigational system represents several improvements over the commercially-available Dexcom CGM systems. The investigational applicator is designed to improve ease of use and reduce the risk of user error compared to Dexcom's G5 commercial device by simplifying the application process. While the commercial device requires the user to perform multiple actions to deploy the sensor-delivery needle, retract the needle, and release the applicator from the transmitter holder, the investigational applicator performs all of these steps with just one action by the user.

The investigational sensor has a lifetime of 10 days, as opposed to the 7-day lifetime of Dexcom's commercial G5 sensor. As a result, users will not need to change their sensors as often, further reducing risk for any difficulties or inconvenience associated with sensor application. The sensor has also been redesigned to reduce sensor error associated with the use of acetaminophen, thus improving the reliability of sensor readings.

Compared to the Dexcom G6 transmitter, the IUO transmitter has a lower design profile to improve everyday wearability.

The mobile (smartphone) app displays glucose information in real-time. To maintain the accuracy of these readings, the system must be calibrated periodically based on fingerstick readings from a blood glucose meter. After initial calibrations, the investigational app requires less frequent calibrations than

the commercial device. While the commercial system requires calibration every 12 hours, after the first day the investigational system requires calibration every 24 hours. This improvement is expected to further improve the usability and acceptance of the CGM system.

During CGM wear, a sterile disposable glucose sensor is applied on the abdomen and held in place with an adhesive. The wire-like sensor is not significantly thicker than the needles used in syringes for insulin injection. The needle insertion depth ranges from 0.35 – 0.55 inches.

Once in place, the sensor pod consists of a glucose oxidase-based electrochemical sensor placed subcutaneously to measure interstitial glucose concentrations over a 40-400 mg/dL range. The transmitter attached to the sensor pod will wirelessly send the sensor's glucose measurements via Bluetooth to a smartphone for display of trends and continuous glucose readings every 5 minutes. Readings will also be stored in the cloud. In using cloud storage, the smartphone also permits protected sharing of data with coaches and other authorized study staff. The smartphone also provides a more user-friendly interface, including larger text. Alerts, alarms, and reminders will be set to minimize disruption for the patient while still supporting proper use of the device and allowing for patient customization.

Participants will need to calibrate their CGM systems using a commercially available blood-glucose meter per manufacturer instructions.

As part of the system's instructions for use, users are informed of the following:

- The system does not replace blood glucose measurements.
- Blood glucose values may differ from sensor glucose readings and the value from the blood glucose meter should be used for treatment decisions.
- Symptoms of high and low glucose should not be ignored. If sensor readings do not fit with symptoms, blood glucose should be measured with a blood glucose meter.

Upon completion of 10 weeks of CGM and activity tracker use, patients will be asked to return their CGM transmitters and unused sensors. Patients may be offered the opportunity to continue to use their smartphones and activity trackers as long as they continue to sync the tracker at least every three weeks through August 31, 2018. During the study, patients can reach out to their coaches as desired by phone and secure text messaging. Likewise, coaches can reach out to patients by phone and secure text messaging. Automated text messages will also be sent to patients as part of the program. Patients will return their smartphones and activity trackers at the end of the program.

